4.2 Secondary Efficacy Endpoints

The secondary efficacy endpoints include the following:

- **EU and RoW:** Proportion of positive pruritus assessments at the patient level over the 72-week treatment period using the Albireo ObsRO instrument.
- **US:** Change from baseline in fasting serum bile acids after 72 weeks of treatment.
- **All Regions:**

- Change from baseline in serum bile acids at Weeks 4, 12, 22, 24, 36, 46, 48, 60, 70, 72, 76 and all visits (every 16 weeks) during the optional extension period.
- Proportion of individual assessments meeting the definition of a positive pruritus assessment at the patient level using the Albireo ObsRO instrument from Weeks 0-4, Weeks 0-12, Weeks 0-22, Weeks 0-24, Weeks 0-36, Weeks 0-46, Weeks 0-48, Weeks 0-60, and Weeks 0-70, and the proportion of positive pruritus assessments at each 4--week interval between Visit 1/Screening and Visit 5/Week 24, then by each visit between Visit 5/Week 24 and Visit 12/Week 76.
- Proportion of individual AM assessments meeting the definition of a positive pruritus assessment at the patient level using the Albireo ObsRO instrument from Weeks 0-4, Weeks 0-12, Weeks 0-22, Weeks 0-24, Weeks 0-36, Weeks 0-46, Weeks 0-48, Weeks 0-60, Weeks 0-70, and Weeks 0-72, and the proportion of positive pruritus assessments at each 4-week interval between Visit 1/Screening and Visit 5/Week 24, then by each visit between Visit 5/Week 24 and Visit 12/Week 76.
- Proportion of individual PM assessments meeting the definition of a positive pruritus assessment at the patient level using the Albireo ObsRO instrument from Weeks 0-4, Weeks 0-12, Weeks 0-22, Weeks 0-24, Weeks 0-36, Weeks 0-46, Weeks 0-48, Weeks 0-60, Weeks 0-70, and Weeks 0-72, and the proportion of positive pruritus assessments at each 4-week interval between Visit 1/Screening and Visit 5/Week 24, then by each visit between Visit 5/Week 24 and Visit 12/Week 76.
- Number of patients undergoing biliary diversion surgery or liver transplantation. These parameters will be evaluated separately and together at Weeks 24, 48, 72 and all visits (every 16 weeks) during the optional extension period.
- Change in growth from baseline to Weeks 12, 24, 36, 48, 60, 72 and all visits (every 16 weeks) during the optional extension period after initiation of odevixibat treatment, defined as the linear growth deficit (height/length

for age, weight for age, and BMI) compared to a standard growth curve (Z-score, StdDev from the fiftieth percentile, P50).

- Change in APRI score and Fib-4 score from baseline to Week 72 and all visits (every 16 weeks) during the optional extension period.
- Change in PELD/MELD score from baseline to Week 72 and all visits (every 16 weeks) during the optional extension period.
- Change in use of UDCA and/or Rifampicin at Weeks 24, 48, and 72.
- Proportion of responders for pruritus scores using the Albireo ObsRO instruments by visit (proportion of patients achieving meaningful reduction based on the clinically meaningful threshold of 1.0 point, which is estimated from the distribution-based and anchor-based approaches in the blinded psychometric analysis)

4.3 Exploratory Endpoints

All Exploratory Endpoints will be evaluated at Weeks 24, 48, and 72 unless otherwise noted. For summary purposes, if not otherwise specified, the baseline value of a parameter is defined as the last non-missing assessment of that parameter before the first dose of odevixibat in Study A4250-008. Exploratory efficacy endpoints include the following:

- Change in serum alanine aminotransferase (ALT), gamma-glutamyl transferase (GGT), and total bilirubin concentration from baseline to Week 72 and all visits (every 16 weeks) during the optional extension period.
- Proportion of individual assessments meeting the definition of a positive pruritus assessment at the patient level over the 72-week treatment period. A positive pruritus assessment includes an itch score ≤ 1 , or at least a 1-point decrease from baseline based on the Albireo PRO instrument; only patients ≥ 8 years of age will complete the Albireo PRO instrument.
- Change from baseline in sleep parameters by each 4-week interval between Visit 1/Screening and Visit 5/Week 24, then by each visit between

Visit 5/Week 24 and Visit 11/Week 72 over the 72-week treatment period measured with the Albireo PRO and ObsRO instruments.

- Change from baseline in international normalised ratio (INR), albumin, liver enzymes, leukocytes, and platelets from baseline to Week 72 and all visits (every 16 weeks) during the optional extension period.
- Change from baseline to all visits where assessed in measures of bile acid synthesis (autotaxin, p-C4)
- Assessment of global symptom relief at Weeks 4, 12, 24, 48, 72 and all visits (every 16 weeks) during the optional extension period as measured by patient, caregiver, and clinician GIC items.
- Change from baseline by each 4-week interval between Visit 1/Screening and Visit 5/Week 24, then by each visit between Visit 5/Week 24 and Visit 12/Week 76 in patient-reported and observer-reported night-time itching and scratching severity scores.
- Change from baseline by week interval from Baseline to Week 72 in patient-reported and observer-reported night-time itching and scratching severity scores.
- Change from baseline by each 4-week interval between Visit 1/Screening and Visit 5/Week 24, then by each visit between Visit 5/Week 24 and Visit 12/Week 76 in patient-reported and observer-reported morning time itching and scratching severity scores.
- Change from baseline by week interval from Baseline to Week 72 in observer-reported morning time itching and scratching severity scores.
- Change from baseline by each 4-week interval between Visit 1/Screening and Visit 5/Week 24, then by each visit between Visit 5/Week 24 and Visit 12/Week 76 in pooled pruritus score including observer-reported scratching for patients <8 years of age and patient-reported itch severity for patients ≥ 8 years of age.

- Change from baseline by week interval from Baseline to Week 72 in pooled pruritus score including observer-reported scratching for patients <8 years of age and patient-reported itch severity for patients ≥ 8 years of age.
- Change from baseline in additional patient-reported and observer-reported sleep parameters (e.g. tiredness, number of awakenings) by each 4-week interval between Visit 1/Screening and Visit 5/Week 24, then by each visit between Visit 5/Week 24 and Visit 12/Week 76.
- Change from baseline in PedsQL questionnaire from Baseline to Week 72 and all visits (every 16 weeks) during the optional extension period.
- Change from baseline in stage of liver fibrosis as assessed by Fibroscan® (where available).
- Change from baseline in stage of liver fibrosis, as assessed by post-treatment biopsy (when available).

4.4 Safety Evaluation

Safety criteria are as follows:

- The primary safety analysis for this study will include the incidence of total treatment-emergent adverse events (TEAEs) and TEAEs categorised by causality, severity, and seriousness assessments made by the Investigator.
- Trends in safety will also be evaluated for the following:
 - Physical examinations
 - Concomitant medications
 - Vital signs
 - Laboratory test results (including clinical chemistry, haematology, urinalysis, alfa-fetoprotein [AFP], vitamins A and E, 25-hydroxy vitamin D, and INR)
 - Abdominal ultrasound
 - Discontinuations due to AEs

5. Sample Size and Power

There is no formal hypothesis testing in this open-label study. The sample size for Cohort 1 was determined in Study A4250-005. For Cohort 1, patients will be enrolled after completion of Study A4250-005 or participation of 12 weeks in that study. For the other endpoints, mainly descriptive analyses will be performed.

The proportion of patients with at least 1 event (i.e., surgical bile diversion, liver transplantation, death) that can be expected in a non-treated population depends on PFIC type and age distribution of the included patients. The expected proportion of patients with events will be calculated for the study population once each patient's age and PFIC type are known, using the probability that a patient will get an event estimated from the reference population in the ongoing observational cohort study, NAtural Course and Prognosis of PFIC and Effect of Biliary Diversion (NAPPED).

As an example, if the expected proportion of patients with at least 1 event is estimated to be 30% in the study population, and then if the proportion of patients with at least 1 event during odevixibat long-term treatment is shown to be only 10% in the study, the power is approximately 89% to 96% (1-sided test, alpha=2.5%) for a confidence interval (CI) with upper boundary <30% based on a sample size of n=48 to 60. The sample size of 60 for Cohort 2 was estimated based on the availability of target patient population to evaluate the therapeutic benefit for those patients.

6. Interim Analysis

This study is an extension study of Study A4250-005 and was ongoing at the time of the New Drug Application (NDA) and Marketing Authorisation Application (MAA) submission in November 2020. For the NDA/MAA submission purposes, the database was locked on 31Aug2020 for Study A4250-005, and an interim analysis of Study A4250-008 with data cut on 15Jul 2020 was performed to accompany the final analyses of Study A4250-005.

For this interim analysis submitted in the NDA/MAA, the analyses described in this SAP were conducted, as appropriate, based on data available at the time of the data cut-off date. The interim analysis was conducted for both safety and efficacy mainly based on descriptive statistics. The main time point was at the end of 24-week treatment period

while all data were included for by-visit summaries. These analyses accompanied the Study A4250-005 analyses and provided further information regarding the safety and efficacy of odevixibat dosing for more than 24 weeks.

For supporting a post-marketing commitment, an interim analysis of Study A4250-008 (planned data cut of 31July2022) was performed in order to update the CSR. The selected analyses described in this SAP were conducted, as appropriate, for the interim analysis based on data available at the time of the data cut-off date. The interim analysis was conducted for both safety and efficacy mainly based on descriptive statistics.

Analyses may be performed at select time points throughout the collection of patient data for regulatory requirements and sponsor decision making purposes.

7. Analysis Sets

The FAS will consist of all patients who received at least 1 dose of study drug in Study A4250-008. The FAS will be the primary analysis set for all analyses unless otherwise specified.

8. Statistical Considerations and Analysis

8.1 Handling of Missing Data and/or Invalid Data and Outliers

8.1.1 Missing Data Analysis Methods for Efficacy Endpoints

No imputation will be made for any missing data. The assessments after intercurrent events (death, or initiation of rescue treatments such as biliary diversion surgery or liver transplantation) or follow-up assessments (\geq last dose day + 15 days) will be excluded from analysis with the exception of the analysis of patients undergoing biliary diversion surgery or liver transplantation. For eDiary data analysis, data after last dose will be excluded from analysis.

9. Statistical Methods

9.1 General Statistical Conventions

Study data will be reviewed periodically (approximately on a quarterly basis) by a DSMB. For DSMB analyses, the Adjudication Process Document outlines the events that

will be adjudicated and see [Section 9.8.2](#). Descriptive statistics are mainly used in this open-label extension study unless otherwise specified. All statistical procedures will be completed using SAS®, Version 9.4 or higher.

Continuous variables will be summarised using descriptive statistics, including the number of patients with non-missing value (n), mean, median, StdDev (or standard error [SE]), minimum, and maximum. The letter “n” will be presented without a decimal point. Minimum and maximum values will be presented to the same precision as in the database. Mean and median will be presented to 1 more decimal place than the minimum and maximum. StdDev or SE will be presented to 1 more decimal place than the mean and median.

For categorical variables, summaries will include counts of patients (frequencies) and percentages. Percentages will be rounded to 1 decimal place. Descriptive summaries of change from baseline in categorical variables will be provided using shift tables, as applicable.

For summary purposes, if not otherwise specified, the baseline value of a parameter is defined as the last non-missing assessment of that parameter before the first dose of odevixibat in Study A4250-008 ([Appendix A](#)). Derived variables used for the analyses are provided in Appendix A.

Analysis windows defined in [Appendix B](#) will be applied for all laboratory parameters, questionnaires, vital sign measurements, physical examinations, and other efficacy parameters in the study, unless otherwise specified.

For the final CSR, all summaries will be presented for the following treatment groups, unless otherwise specified.

- Placebo (A4250-005) to Odevixibat (A4250-008)
- Odevixibat 40 or 120 µg/kg/day (A4250-005) to Odevixibat 120 µg/kg/day (A4250-008)
- Cohort 2 (A4250-008)
- Odevixibat Overall

Table header will be presented as follows:

Placebo/Odevixibat ^a (A4250-005/A4250-008)	Odevixibat/Odevixibat ^b (A4250-005/A4250-008)	Cohort 2 ^c (A4250-008)	Odevixibat Overall
--	---	--------------------------------------	-----------------------

a Includes patients who received placebo in Study A4250-005 and transitioned to odevixibat 120 µg/kg/day in Study A4250-008

b Includes patients who received odevixibat 40 or 120 µg/kg/day in Study A4250-005 and transitioned to odevixibat 120 µg/kg/day in Study A4250-008

c Includes patients who received odevixibat in Cohort 2 of Study A4250-008

All patient data, including derived data, will be presented in individual patient data listings. All listings will be sorted by cohort/treatment subgroup, patient number, date/time, and visit. The sex and age for each patient will be stated on each listing. Data listings will be based on all enrolled patients.

Patients who didn't directly rollover from Study A4250-005 but enrolled in Study A4250-008 after a gap in dosing or re-enrolled in Study A4250-008 after a gap in dosing were assigned separate patient IDs. They will be considered as separate patients in all analyses.

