9.6.3 Analyses of Primary Efficacy Endpoints

All the primary analyses will be based on the FAS, unless otherwise specified.

For the EU and RoW, change from baseline 2 in fasting serum bile acids will be analysed by using the 1-sample t-test or the Wilcoxon signed rank test, as appropriate at the end of the 72-week treatment period based on the average of the values at Weeks 70 and 72. Baseline 2, defined in the table of derived variables in [Appendix A](#), will be used to calculate change from baseline for the summary.

For Cohort 1 patients who were on odevixibat in Study A4250-005, change from Baseline 1 to end of the 72-week treatment in Study A4250-008 will be analysed by using the 1-sample t-test or the Wilcoxon signed rank test, as appropriate. Baseline 1,

defined in the table of derived variables in [Appendix A](#), will be used for this statistical analysis.

For the US, the proportion of positive pruritus assessments at the patient level over the 72-week treatment period using the Albireo ObsRO instrument will be summarised descriptively. A positive pruritus assessment is defined as a scratching score of ≤ 1 or at least a 1-point drop from baseline on the Albireo ObsRO instrument. At each assessment, the AM score will be compared to the baseline AM average, and the PM score will be compared to the baseline PM average. Both AM and PM pruritus assessments will be included in the analysis of this endpoint. For analysis purposes, diary entries will be assigned to a study day based on the recorded date regardless of recorded time. AM scores from the period of 14 days before or on the first dose day in Study A4250-008 will be averaged as AM baseline. PM scores from the period of 14 days before the first dose day in Study A4250-008 will be averaged as PM baseline. If a patient's baseline score is ≤ 1 , then only the criterion of a one-point drop from baseline on the Albireo ObsRO instrument will be used to determine whether a pruritus assessment is positive or not for the primary endpoint analysis. Rounded baseline score will be used for the analysis.

A 95% CI will be provided for the proportion of positive pruritus assessments.

Change from Baseline 1 and 2 in monthly scratching severity score to end of the 72-week treatment in Study A4250-008 will be analysed by using the 1-sample t-test or the Wilcoxon signed rank test, as appropriate. Baseline 1 will only be used for patients in Cohort 1 who were on odevixibat in Study A4250-005.

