⁸ <https://www.cdc.gov/nccdphp/dnpao/growthcharts/resources/sas-who.htm> following WHO's method

⁹ Abdel-Rahman, Susan M et al. "Construction of Lambda, Mu, Sigma Values for Determining Mid-Upper Arm Circumference z Scores in U.S. Children Aged 2 Months Through 18 Years." *Nutrition in clinical practice* : official publication of the American Society for Parenteral and Enteral Nutrition vol. 32,1 (2017): 68-76.

The number and percent of patients achieving positive pruritus assessment for more than 50% of the time will be summarised by treatment group. Both AM and PM pruritus assessments will be included in the analysis of this endpoint. A cumulative distribution function (CDF) plot showing proportions of patients achieving positive pruritus assessment for more than X% of the time, X is the time of achieving positive pruritus assessment from 0 to 100%, by treatment group will be provided.

❖ Proportion of Responders for Pruritus Scores

The proportion of responders for pruritus scores will be tabulated by visit based on monthly scores and bi-weekly scores. The 95% CI of the proportion of responders will be provided, based on the exact method of Clopper-Pearson. A responder is defined as a patient who reports a decrease in pruritus score from unrounded baseline equivalent to or greater than the threshold of meaningful change estimated from the blinded psychometric analysis; the results of the blinded psychometric analysis across all anchors support a threshold of 1.0 point for AM, PM and AM and PM scratching scores. Baseline 1 and 2, defined in the table of derived variables in [Appendix A](#), will be used for data analysis. Baseline 1 will only be used for patients in Cohort 1 who were on odevixibat in Study A4250-005.

❖ Biliary Diversion Surgery and Liver Transplantation

Number and percent of patients undergoing biliary diversion surgery and/or liver transplantation will be summarised by using descriptive statistics. A 95% CI also will be presented for the corresponding percentage. These parameters will be evaluated separately and together at Weeks 24, 48, 72 and all visits (every 16 weeks) during the optional extension period.

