Kaplan-Meier curves will be used when appropriate for time-to-event data (that is, time to biliary diversion surgery or liver transplantation or death and time to any event). If a patient does not have any event, the patient will be censored at the last contact date. Median event-free times and associated 95% CIs will be calculated using Brookmeyer and Crowley methodology and a log-log transformation for constructing CIs.

❖ Fibroscan®

The change in APRI and Fib-4 score will be summarised using descriptive statistics from baseline 2 to Week 72 and all visits (every 16 weeks) during the optional extension period.

❖ PELD and MELD Score

The change in PELD and MELD will be summarised separately using descriptive statistics from baseline 2 to Week 72 and all visits (every 16 weeks) during the optional extension period.

❖ UDCA and/or Rifampicin

Percentages of patients in use of UDCA and/or Rifampicin at weeks 24, 48, and 72 will be presented in 4 categories, use of UDCA, use of Rifampicin, use of UDCA or Rifampicin, use of UDCA and Rifampicin. Percentage will be based on patients in study at week 24, 48, and 72.

Shift tables from Baseline 2 in use of UDCA and/or Rifampicin at Weeks 24, 48, and 72 will be presented in the following categories. “None”, “UDCA alone”, “Rifampicin alone”, “UDCA and Rifampicin”, “Early Termination”. Percentage will be based on patients in study at week 24, 48, and 72.

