	The number of capsules planned to be taken will be estimated based on patient's body weight per Protocol Table 3. If a patient's weight changes at any time during the study, dose adjustment will be required.
Derivations for Efficacy Parameters	
Baseline (general)	
Baseline 1 is defined as the last value prior to the first dose in Study A4250-005 for patients in Cohort 1.
 
Baseline 2 is defined as the last value prior to the first dose in Study A4250-008 for all patients. For patients in Cohort 1, the pre-dose assessments of Study A4250-008 can be from Study A4250-005.
 
Baseline 2 will be used in all analyses unless otherwise specified.

Baseline for serum bile acids change from baseline	
Baseline 1 is defined for patients in Cohort 1 and will be calculated as the average of last 2 values prior to the first dose in Study A4250-005. If only one non-missing value is available, it will be used as baseline.
 
Baseline 2 is defined as follows:
 
Cohort 1: the average of the last 2 values before the first dose of study drug in Study A4250-008. In general, these 2 values are the values of the last 2 assessments of Study A4250-005. If pre-dose assessments are collected in Study A4250-008 for a patient, then the values of pre-dose assessments in Study A4250-008 will be considered first and used to calculate the baseline. These 2 values need to be taken from 2 consecutive scheduled visits or unscheduled visits. If only one value is available from 2 consecutive scheduled visits or unscheduled visits, then that value will be used as baseline.
 
Cohort 2: the average of last 2 values prior to the first dose in Study A4250-008. If only one non-missing value is available, it will be used as baseline.
 
Baseline 2 will be used in all analyses unless otherwise specified.

End value for serum bile acids change from baseline	The end value is the average of the values at Weeks 70 and 72 after the start of treatment. (Appendix B). If one value is missing, then the non-missing value will be used as the end value. If both values are missing, then the end value is missing.

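### A person who re-enrols in A4250-008 under a second ID is counted as two patients in all analyses, with no person-level count or sensitivity analysis

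*SAP*

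**What the plan says.** SAP Section 9.1 describes two groups that had a gap in dosing: those who came late from Study A4250-005, and those who "re-enrolled in Study A4250-008 after a gap in dosing were assigned separate patient IDs". For both, the instruction is: "They will be considered as separate patients in all analyses". Only the second group can hold two A4250-008 IDs.

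Section 7 sets no limit of one record per person: "The FAS will consist of all patients who received at least 1 dose of study drug in Study A4250-008". Sections 9.6 and 9.7 use this set for efficacy and safety.

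The methods applied to it treat each ID as an independent patient:

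- Section 9.6.3, bile acids: "change from baseline 2 in fasting serum bile acids will be analysed by using the 1-sample t-test or the Wilcoxon signed rank test".
- Section 9.6.4, pruritus responders: "The 95% CI of the proportion of responders will be provided, based on the exact method of Clopper-Pearson".
- Section 9.6.4, surgery and transplantation: "A 95% CI also will be presented for the corresponding percentage".
- Section 9.6.4, time to event: "If a patient does not have any event, the patient will be censored at the last contact date".
- Section 9.7.1 counts a patient once per preferred term and once per system organ class, but this works within an ID.

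The SAP gives no first-enrolment set, no person-level clustering term, no sensitivity analysis and no count of persons with two IDs.

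**The concern.** Two courses in the same person are not two independent patients. Where both IDs were dosed:

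- the person adds two to the denominators for AE incidence and for surgery or transplantation, while an event may be recorded under one ID or both;
- in the disposition table of Section 9.2, the same person can appear both as stopping early and as completing 72 weeks;
- in the Kaplan-Meier analysis, the second ID starts again at time zero for someone already known to be event-free, which tends to favour the drug;
- by-visit summaries and confidence intervals treat correlated values as independent, so the stated precision is too high.

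In a mainly descriptive study of a rare disease, patient counts, percentages and intervals are the main product. They should refer to persons.

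**Working it through.** **Inputs from the SAP.** Section 5 gives a reference event proportion of 30%, an on-treatment proportion of 10%, one-sided alpha of 2.5%, n = 48 to 60, and stated power of about 89% to 96%. It also gives 60 as the Cohort 2 size.

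**Assumed, because the SAP does not give them.** Number of persons with two A4250-008 IDs, k = 1 to 6; within-person correlation, rho = 0.3 to 0.8.

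**1. The plan's own figure.** Exact binomial power with a Clopper-Pearson upper bound below 30%:
- n = 48 allows at most 7 events: power 89.8%.
- n = 60 allows at most 10 events: power 96.6%.

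The stated power is reproduced and is not in dispute.

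**2. Inflated denominator, each event recorded once.** The reported percentage is x/(60 + k). With x = 6:
- k = 0: 6/60 = 10.0% (95% CI 3.8 to 20.5)
- k = 1: 6/61 = 9.8% (3.7 to 20.2)
- k = 3: 6/63 = 9.5% (3.6 to 19.6)
- k = 6: 6/66 = 9.1% (3.4 to 18.7)

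With x = 18, 30.0% becomes 29.5% at k = 1 and 27.3% at k = 6.

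**3. The other direction.** If one re-enrolled person has the same AE in both courses, the report is (6 + 1)/(60 + 1) = 11.5% instead of 10.0%. AE incidence can therefore move either way.

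**4. One-sample t-test, only if both courses supply a value.** With N records of which k persons supply two, the variance is understated by the factor 1 + 2·k·rho/N. The true level of a nominal two-sided 5% test is 2·[1 − Φ(1.96/√factor)].
- N = 60, k = 1, rho = 0.3: factor 1.010, level 5.1%
- N = 60, k = 6, rho = 0.8: factor 1.160, level 6.9%
- N = 48, k = 6, rho = 0.8: factor 1.200, level 7.4%

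**5. When can both courses enter the 72-week analyses?** For bile acids, Appendix A averages Weeks 70 and 72 and states: "If both values are missing, then the end value is missing". Table 4 opens the Week 70 window at day 456, and Section 8.1.1 imputes nothing. For pruritus over Weeks 0 to 72, Table 10 requires at least half of the expected diary data in Weeks 71 to 72. A first course that ended before day 456 drops out of both, so double entry needs two courses that each run to about Week 70.

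**6. Exact one-sided error of the 30% rule** with 60 records and fully concordant pairs: 1.39% at k = 0, 1.51% at k = 1, 2.21% at k = 6. All stay below 2.5%.

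**7. Kaplan-Meier.** An event-free first ID is censored at last contact. Section 3.1 plans three-monthly calls up to Week 72 after early discontinuation, and Section 8.1.1 exempts the surgery/transplant analysis from its post-treatment exclusions. The first record may thus run past the treatment stop. The SAP does not say whether contact after re-enrolment, or an event at that time, belongs to one ID or both. In either case the second record begins at time zero.

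**The case against.** The strongest reply is that little depends on this. Section 5 says there is no formal hypothesis testing, no success rule rests on the nominal p-values, and Section 10 moves the comparison with the NAPPED population outside this SAP. The rule is stated openly, and all patient data are listed. The number affected is unknown and may be very small. The base of 60 is the Cohort 2 target alone, and the overall column adds Cohort 1, which dilutes the effect. All of this stands and limits the size of the point. It does not make one person two patients in a percentage or a survival curve.

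A reader might also infer more than the SAP supports:

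- **That re-enrolled persons always count twice in the primary tests.** They do so only if both courses have qualifying data near Weeks 70 to 72.
- **That the first record is cut at treatment stop in the Kaplan-Meier analysis.** The rule is last contact, with calls planned to Week 72.
- **That a new, worse baseline flatters the second course.** A second ID does get a new Baseline 2 after earlier odevixibat exposure, but nothing in the SAP describes how these persons fared in the gap.
- **That bias is as large as the share of paired records.** At k = 5 that share is 2 × 5/65 = 15.4%, but it is not a bias. The effects above are much smaller.

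The choice of replacement is partly a matter of judgement: follow-up through the gap includes time off drug, and a first-enrolment rule sets aside second-course data.

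**Conclusion.** The point holds in a limited form. By the SAP's stated rule, a person dosed under two A4250-008 IDs enters the FAS twice. That double-counts the person in AE, surgery/transplant and disposition denominators, in Kaplan-Meier estimates, and in by-visit summaries and intervals. In the 72-week bile acid and pruritus analyses it is conditional on late data under both IDs.

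Under the assumed 1 to 6 re-enrolled persons in about 60, the effect is small: less than one percentage point at a 10% event rate when events are recorded once, and a t-test level of about 5.1% to 6.9% at N = 60 if every pair contributes. The direction is not fixed for AEs. The true size cannot be stated until the number re-enrolled is known. The correction is worth making because the rule is explicit, no sensitivity analysis covers it, and the repair is cheap.

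**What to change.** Replace the last sentence on this matter in Section 9.1 with person-level rules, and align Sections 7, 9.2, 9.6.4 and 9.7:

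- Link all A4250-008 IDs to a unique person and report how many persons hold two.
- Count each person once in AE incidence, surgery/transplant percentages and disposition.
- Use the first A4250-008 enrolment for the main efficacy analyses.
- Run time to surgery, transplantation or death from the first A4250-008 dose to last contact under either ID, and state that this includes the off-drug gap.
- List second courses, and show the two-ID version as a sensitivity analysis.

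The cost is a wording change and an ID-link table. n falls by the number re-enrolled, and second-course efficacy data move to the sensitivity analysis.
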